5.3.2.2. Pediatric RSV Electronic Severity and Outcome Rating System (PRESORS)

With reference to the definitions and derivations detailed in Section 5.3.1.2.1, the following will be presented.

ObsRO Concept, Summary Parameter and Daily Scores; ClinRO Concept, Summary Parameter and Daily Scores

Descriptive statistics will be shown for the actual values and changes from baseline by analysis visit and by treatment group. Descriptive statistics will include the number of subjects, mean, standard deviation, standard error, 95% confidence interval, median, range and interquartile range. Descriptive statistics will be presented overall, and by subgroup (as defined in Section 2.4). For analyses for which we need at most one assessment per day (e.g. for summarizing combined in- and outpatient data captured by the clinician), we take the worst over 24 hours according to Table 6.

Graphical presentation of actual values and changes from baseline for individual concept scores and/or summary parameters (daily summary score [worst of the average]) over time will include:

- Mean (SE)
- BAR plots including:
 - Baseline PRESORS ObsRO/ClinRO
 - Subset of hospitalized subjects (Cohort 1): last PRESORS ObsRO/ClinRO concept scores BEFORE hospital discharge
 - Subset of hospitalized subjects (Cohort 1): first PRESORS ObsRO/ClinRO concept scores AFTER hospital discharge
- Individual subject profiles over time: key RSV symptoms

The aforementioned will be presented overall by treatment group and by the subgroups as defined in Section 2.4.

To explore the agreement between the two approaches (refer to Table 17 in Section 5.3.1.2.1), in identifying the worst concept score per day, used in deriving the four summary parameter daily summary scores, the actual values and changes from baseline summary scores over time will be presented graphically for each summary parameter individually (x4):

- Overlay of primary and secondary approach of Mean±SE daily summary scores over time on one plot:
 - **Average of the worst (PRIMARY APPROACH)**
 - **Worst of the average (SECONDARY APPROACH)**

The aforementioned will be presented overall by treatment group only.

Association Between Summary Parameter Score: PRESORS ObsRO Key RSV Symptoms and Covariates/Baseline Indicators

The potential association between the change from baseline in summary scores of the summary parameter, PRESORS ObsRO: key RSV symptoms and the covariates and/or baseline indicators of interest will be explored over time at Day X, Day 8 and Day 10 in a similar manner, utilizing multiple regression with backward stepwise elimination, as described for the RSV RNA viral load. Refer to Section [5.3.2.1](#) for details.

Day X is defined as the day when at least 50% of Cohort 1 subjects, across all treatment groups, have been discharged from hospital. The day identified will be used for both cohorts.

PRESORS ObsRO: Change from Baseline: Mixed Model Repeated Measures

For the summary parameter, PRESORS ObsRO: key RSV symptoms, change from baseline over time (average of the worst [primary approach] daily summary scores) will be analyzed using a restricted maximum likelihood based repeated measures approach. The analysis model will include fixed (discrete) effect parameters for treatment, randomization stratification factors (derived), analysis visit and treatment-by-analysis visit interaction, as well as continuous covariates for the baseline summary parameter score and baseline summary parameter score-by-analysis visit interaction. An unstructured covariance structure will be selected to model the within-subject errors. In case this model will not converge, the Toeplitz covariance structure will be applied. The Kenward-Roger approximation will be used to estimate the denominator degrees of freedom.

Differences between treatment groups and by analysis visit will be determined using appropriate contrasts. Both the 80% and 95% 2-sided confidence intervals will be presented.

For subgroup analyses, the model will also include the subgroup variable as a covariate and the subgroup-by-treatment, subgroup-by-analysis visit and subgroup-by-analysis visit-by-treatment interactions. For details about subgroups refer to Section [2.4](#).

Time to Resolution of Symptoms (Concepts) and Four Summary Parameters: Key RSV Symptoms, Respiratory Symptoms, General Illness Behavior and Overall RSV Symptoms (ObsRO)

For the RSV symptoms (concepts) and four summary parameters, these time to event variables will be analyzed using Kaplan-Meier analysis. Both the 80% and 95% 2-sided confidence intervals will be presented.

The aforementioned will be presented overall by treatment group and by the subgroups as defined in Section 2.4, for summary parameters, key RSV symptoms and overall RSV symptoms only.

For time to resolution of summary parameters, key RSV symptoms and overall RSV symptoms (ObsRO), sensitivity analyses will be performed considering 4 different imputation methods:

- Method 1: from first resolution (score 0 or 1) after last unresolved value onwards, impute missing data as resolved.

- Method 2: impute all missing values as unresolved (score >1).
- Method 3: impute all missing values in-between resolved observations (score 0 or 1) as resolved.
- Method 4: impute all missing values as unresolved (score >1), except when in-between resolved values where resolved is imputed.

These sensitivity analyses will be provided from IA#3 onwards.

In addition, for the summary parameters, key RSV symptoms and overall RSV symptoms, difference in median time (hours) to resolution (event) between each active treatment group as compared to placebo will be investigated using the AFT model with log-logistic distribution. The model will include class variables treatment group with placebo as reference and randomization stratification factors (derived) and baseline summary parameter score. Summary will include parameter estimates and associated standard error, covariance matrix of parameter estimates, estimated accelerated failure time ratio (as compared to placebo) and both 80% and 95% 2-sided confidence intervals.

The aforementioned will be presented overall by treatment group and by the subgroups as defined in Section 2.4.

Parameter estimates and associated variance matrix resulting from AFT model, will be used in a generalized MCP-Mod approach to test dose-response, at 1-sided alpha level=0.10. The aforementioned MCP-Mod will be presented overall by treatment group only.

Graphical presentation will include:

- Overlay of survival curves with Kaplan-Meier survival function and AFT on one plot
- Forest plot of accelerated failure time ratios and resulting confidence intervals for subgroups of interest as defined in Section 2.4 including the relevant subgroup variable as covariate in the model with subgroup*treatment group interaction.

Status of RSV Symptoms, Status of Health, Status of Improvement of RSV Symptoms, Status of Return to Pre-RSV Disease Health (ObsRO)

The proportion of subjects within the categories will be shown in a frequency tabulation, as well as graphically, per analysis timepoint, per treatment group and analysis visit. Subjects with missing data at that analysis visit will not be counted in the denominator for the proportion. Additionally, 95% 2-sided confidence interval for each binomial proportion within the individual categories will be presented as based on the Wilson score test.

The aforementioned will be presented overall by treatment group and by the subgroups as defined in Section 2.4.

Status of Overall Condition, Status of Health, Health Compared to the Baseline Assessment (ClinRO)

The proportion of subjects within the categories will be summarized in a similar manner as described for aforementioned ObsRO ‘status’ variables.

Missing Data: Caregiver/Clinician PRESORS, Number of Caregivers/Investigators

Summary of the number (n) and percentage (%) of subjects with at least one completed assessment by analysis visit window (baseline to Day 21), for subjects still ongoing in the study at the timepoint of interest, will be presented overall by treatment group and cohort.

Total number of subjects with completed assessments from baseline to Day 21 will be evaluated relative to the total number of subjects with expected assessments taking into account the protocol-required assessment schedule.

Actual number of subjects with assessments missing per analysis visit window, taking into account the protocol-required assessment schedule and subject status (hospitalized vs outpatient) at the timepoint of interest, will also be presented.

The number of caregivers and investigators per subject, over the entire study course, will be presented as a frequency tabulation.

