5.2.3. Analysis Method

Mean \log_{10} RSV RNA viral load values over time will be analyzed using a restricted maximum likelihood based repeated measures approach (MMRM). The analysis model includes fixed (discrete) effect parameters for treatment, randomization stratification factors (derived), analysis visit and treatment-by-analysis visit interaction, as well as continuous covariates for baseline \log_{10} viral load and baseline \log_{10} viral load-by-analysis visit interaction. An unstructured (co)variance structure will be used to model the within-subject errors. In case this model will not converge, the Toeplitz covariance structure will be applied. The Kenward-Roger approximation will be used to estimate the denominator degrees of freedom.

For subgroup analyses, the model will also include the subgroup variable as a covariate and the subgroup-by-treatment, subgroup-by-analysis visit and subgroup-by-analysis visit-by-treatment interactions. For details about subgroups please see Section 2.4.

A generalized MCP-Mod (1) approach at 1-sided alpha-level of 2.5% will be applied based on the estimated AUC treatment group effect and variance covariance matrix. Candidate models are given by the EMax (0.40428), Exponential (0.36411) and Linear model, with the aim to test for existence of drug-related effects. Each of the dose-response shapes in the candidate set will be tested using the corresponding contrast t-test statistic, employing a critical value derived for the maximum of the t-test statistics (based on the associated multivariate t-distribution) to ensure appropriate multiplicity correction that preserves a 1-sided 0.025 Type I error rate. A dose-response trend is established when the maximum of the t-test statistics exceeds the critical value.

MCP-Mod uses dose levels 0, 3 and 9 mg/kg which correspond to Placebo, Low and High dose respectively according to the dose/kg for age-group 3 as described in Section 1.2.

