factors are deleted one-by-one until a stopping condition is satisfied. At each step, the factor showing the smallest contribution to the model is eliminated. The parameter estimates along with the 95% 2-sided confidence limits by predictor variable will be produced. In addition, residual plots and goodness of fit measures will be evaluated, but not displayed in output. The SAS® procedure GLM SELECT (selection = backward SLS = 0.1) will be used. The procedure removes factors based on significance level and stops when all factors in the model are significant at the 0.1 level.

Predictor variables which show a strong association may further be explored as additional covariates in the primary efficacy model described in Section [5.2.3](#).

RSV RNA Viral Load AUC

A similar model as used for the primary analysis will be used for the RSV RNA viral load AUC until Day 3 and until Day 8. The differences in these AUCs for active versus placebo will be derived using appropriate contrasts for both Day 3 and Day 8 and from the same model containing all RSV RNA viral load assessments from baseline through Day 8.

Least squares mean estimates of the treatment differences, including the 95% 2-sided confidence intervals, will be presented.

For subgroup analyses, the model will also include subgroup variable as covariate, subgroup-by-treatment, subgroup-by-analysis visit and subgroup-by-analysis visit-by-treatment interactions. For details about subgroups refer to Section [2.4](#).

The individual AUCs until Day 14, derived using the trapezoidal method, will be analyzed using a generalized linear model with $AUC_{Day14/0-312h}$ as a dependent variable, treatment group and randomization stratification factors (derived) as fixed factors, and baseline \log_{10} RSV RNA viral load as fixed covariate. The differences versus placebo will be estimated using appropriate contrasts and presented with 95% 2-sided confidence intervals.

Proportion of Subjects with Undetectable RSV RNA Viral Load

The proportion of subjects within the RSV RNA viral load categories (undetectable, detectable and quantifiable) will be shown in a frequency tabulation, as well as graphically, by treatment group and analysis visit. Subjects with missing data at that analysis visit will not be counted in the denominator for the proportion. Additionally, 95% 2-sided confidence interval for each binomial proportion within the individual categories will be presented as based on the Wilson score test.

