- The conditional power at IA#4 is $<50\%$ to demonstrate antiviral activity of JNJ-53718678 compared with placebo based on the MCP-Mod trend test on viral load at 1-sided alpha=2.5% based on combined data from Cohort 1 and Cohort 2.

AND

- 80% 2-sided confidence interval on at least 2 key clinical course endpoints excludes effects as good as the TV based on data from Cohort 2 only

AND

- None of the 80% 2-sided confidence intervals on any key clinical course endpoint excludes effects as bad as the MAV based on data from Cohort 2 only

For viral load, the conditional probability of success at IA#4 using combined data from Cohorts 1 and 2 will be calculated assuming i) no enrichment and ii) enrichment as described below.

In both cases, the conditional probability of success will be set to 1 if the 1-sided p-value for the MCP-Mod trend test is less than 2.5% at IA#3, as success has already been reached. Otherwise, the conditional Type I error will be calculated using the inverse-normal combination approach:

$$\rho = 1 - \Phi \left(\frac{\Phi^{-1}(0.975) - \sqrt{w_1} \Phi^{-1}(1 - p_{Full})}{\sqrt{1 - w_1}} \right)$$

where:

- p_{Full} represents the 1-sided p-value for the MCP-Mod trend test for the full population at IA#3
- $w_1 = n_1 / n$
- n_1 represents the total number of randomized patients in Cohorts 1 and 2 at the time of IA#3
- $n = 294$, the planned total number of randomized patients in Cohorts 1 and 2 at IA#4

Given the conditional Type I error, the critical value for the MCP-Mod test based on new data from IA#4 only will be calculated. The conditional probability of success at IA#4 will be calculated under the observed test statistic at IA#3 (Z_1), adjusted for the sample size of the new data at IA#4 as:

$$CP_x = 1 - P(\bigcap_{i=1}^3 \{Z_{i,2} \in (-\infty, CRV)\})$$

where:

$$Z_2 \sim N \left(\mu_{Z,2} = \sqrt{\frac{n_2}{n_{1,x}}} Z_{1,x}, corr = corr_{MCPx} \right)$$

and:

- x corresponds to the decision not to enrich / to enrich at IA#3
- $Z_{1,x}$ represents the vector of observed MCP-Mod test statistics at IA#3 (Linear, Emax and Exponential models) based on the population of interest (full population for no enrichment and the sub-population with symptom onset ≤ 3 days for enrichment).
- Z_2 represents the vector of observed MCP-Mod test statistics for the second stage.
- $Z_{i,2}$ represents the observed MCP-Mod test statistic for the second stage (based on the new data at IA#4) for model i.

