- The time to resolution of key RSV symptoms will be analyzed using an accelerated failure time (AFT) model, using the log-logistic distribution as described in Section 5.3.2.2. However, the term for baseline \log_{10} viral load will be retained whether or not it is significant at the 10% significance level. The median time to resolution for the placebo group (T_p) in days will be estimated based upon this model and the TV that corresponds to a 1-day reduction for the high dose group will be calculated as a log relative reduction (i.e. as $\log[(T_p-1)/T_p]$). The MAV of no difference corresponds to a log relative reduction of $\log(T_p/T_p) = 0$. The 1-sided p-values for the tests to compare the difference between the high dose and placebo groups versus the TV and MAV will be derived using normal approximations for appropriate contrasts, Z_{TV} and Z_{MAV} .

Change from baseline in key RSV symptoms at Day 8

- The change from baseline in key RSV symptoms at Day 8 will be analyzed using a restricted maximum likelihood repeated measures approach as described in Section

5.3.2.2. The adjusted mean reduction from baseline for the placebo group will be estimated based upon this model (\bar{x}_P) and the TV that corresponds to a 20% larger change from baseline for the high dose group (i.e. $1.2\bar{x}_P$) will be calculated. The MAV corresponds to a difference in the change from baseline of 0 (i.e. $1.0\bar{x}_P$). The 1-sided p-values for the tests to compare the difference between the high dose and placebo groups versus the TV and MAV will be derived using normal approximations for appropriate contrasts, Z_{TV} and Z_{MAV} .

Incidence of RSV-related complications

- The 1-sided p-values to compare the proportion of subjects with at least one RSV-related complication between the high dose and placebo groups versus the MAV and TV will be derived using a normal approximation to the binomial distribution; where:

$$\hat{p}_1 - \hat{p}_2 \sim N \left(p_1 - p_2, \frac{p_1(1-p_1)}{n_1} + \frac{p_2(1-p_2)}{n_2} \right)$$

The TV of an absolute reduction in rate of 10% corresponds to a difference in the proportion of subjects with at least one RSV-related complication in high dose versus placebo of -0.1. The MAV corresponds to a difference in the proportions of 0.

For each of the three clinical course endpoints, the conditional probability for the Stop decision for the situation without/with enrichment and for each assumed total sample size will be calculated as:

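### The only covariance fallback for the repeated-measures models is an unqualified Toeplitz, which as usually read assumes equal variance at every visit and can misstate the Day 8 symptom standard error if it is ever used

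*SAP*

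**What the plan says.** Both repeated-measures models start from an unstructured matrix. For viral load, SAP Section 5.2.3 states "An unstructured (co)variance structure will be used to model the within-subject errors". For the key RSV symptoms score, Section 5.3.2.2 states "An unstructured covariance structure will be selected to model the within-subject errors". Both sections then give the same single fallback: "In case this model will not converge, the Toeplitz covariance structure will be applied". Inference in both is by Kenward-Roger: "The Kenward-Roger approximation will be used to estimate the denominator degrees of freedom".

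Neither section says whether the Toeplitz is homogeneous or heterogeneous, names a next step, or mentions an empirical variance. The three sensitivity analyses of the primary endpoint in Section 5.2.3.1 do not vary the covariance.

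The estimates are used as follows:
- **AUC to Day 5.** The MCP-Mod test "will be applied based on the estimated AUC treatment group effect and variance covariance matrix".
- **AUC to Day 3 and Day 8.** Section 5.3.2.1 takes these "from the same model containing all RSV RNA viral load assessments from baseline through Day 8". Section 5.2.3 does not list the visits in the primary model.
- **Day 8 symptoms.** In Section 5.6, "The change from baseline in key RSV symptoms at Day 8 will be analyzed using a restricted maximum likelihood repeated measures approach". The resulting contrasts against the target value (TV) and minimum acceptable value (MAV) enter the conditional probabilities at IA#3. One limb of the IA#3 and IA#4 futility rule is that the "80% 2-sided confidence interval on at least 2 key clinical course endpoints excludes effects as good as the TV".

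**The concern.** Plain Toeplitz lets correlation depend on the lag between visits but holds the variance constant. Kenward-Roger adjusts for small-sample estimation within the assumed structure; it does not repair a wrong one. If the true variances differ by visit, the model pools them, and the standard error at a single visit can be too small or too large.

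Unequal variances are plausible for both outcomes. The symptom score is bounded between 0 and 3 and should fall toward zero as children recover. In viral load, a target-not-detected result is set to 0 log10 against 2.15 or 2.90 for detected but non-quantifiable (Section 5.1.2), so the spread may change as children clear virus.

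The fallback could also be needed. Caregiver scores run daily to Day 21, and Section 5.3.2.2 does not limit the visits. If Days 2-21 all enter, there are 20 visits and 20 × 21 / 2 = 210 covariance parameters. At IA#3 these would be fitted to about 70 to 80 Cohort 2 children, and the analysis is repeated in the subgroup with symptom onset within 3 days.

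At stake are the accuracy of one of three key clinical inputs to the IA#3 and IA#4 decisions and, to a lesser degree, precision on the primary endpoint.

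**Working it through.** **The plan's own figures.** The SAP gives no figure for the fallback and no visit-specific variances or correlations. Its Table 1 power for MCP-Mod (74 per arm, CV 35%, 20% reduction, 1-sided 2.5%, doses 0/3/9) reproduces at 92.3 / 95.3 / 96.6%, but that does not bear on the covariance structure.

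**Assumptions.** Complete data; SD linear in visit day; lag correlation 0.6 or 0.8 per day. With equal variances the error is zero.

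**Day 8 symptom contrast.** The true SE is proportional to the Day 8 SD. Under a common variance, the model SE is approximately proportional to the root-mean-square SD over the visits fitted. For n evenly spaced SDs, RMS² = mean² + step² × (n² − 1)/12. Coverage of the 80% interval = 2Φ(1.2816 × model SE / true SE) − 1.

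| SD over Days 2-21 | Day 8 SD | Model visits | RMS SD | Model/true | 80% coverage |
|---|---|---|---|---|---|
| 0.45 to 0.20 | 0.45 − 6 × 0.25/19 = 0.371 | Days 2-21 | √(0.325² + 0.01316² × 33.25) = 0.334 | 0.90 | 75% |
| 0.25 to 0.45 | 0.25 + 6 × 0.20/19 = 0.313 | Days 2-21 | √(0.350² + 0.01053² × 33.25) = 0.355 | 1.13 | 85% |
| 0.45 to 0.20 | 0.371 | Days 2-8 | √(0.4105² + 0.01316² × 4) = 0.411 | 1.11 | 85% |
| 0.25 to 0.45 | 0.313 | Days 2-8 | √(0.2816² + 0.01053² × 4) = 0.282 | 0.90 | 75% |

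Projecting the true matrix onto homogeneous Toeplitz by likelihood (the large-sample limit of the fit) gives the same picture: 0.90 and 1.14 for Days 2-21, 1.11 and 0.90 for Days 2-8. The same trend therefore errs in opposite directions depending on where the model stops, which the SAP does not fix.

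Other assumed trends over Days 2-8: if variance doubles by Day 8, the ratio is 0.87 and coverage 73%; if it halves, 1.22 and 88%.

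**AUC to Day 5.** Assume SD rises from 0.9 at Day 2 to 1.8 at Day 8, so Days 2-5 have 0.90, 1.05, 1.20, 1.35. Trapezoid weights (in days) are 1, 1, 1, 0.5. With lag correlation 0.8:
- True: w′Σw = 3.808 + 2 × (2.412 + 1.145 + 0.311) = 11.54, root 3.398.
- Same correlations with unit variance: 3.25 + 2 × (2.00 + 0.96 + 0.256) = 9.682, root 3.112.
- Days 2-5 model: RMS SD = √(1.125² + 0.15² × 1.25) = 1.137; 1.137 × 3.112 = 3.54; ratio 1.04.
- Days 2-8 model: RMS SD = √(1.35² + 0.15² × 4) = 1.383; 1.383 × 3.112 = 4.30; ratio 1.27.

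The likelihood projection gives 1.04 and 1.27-1.28. For a single contrast, a nominal 1-sided 2.5% test would run at Φ(−1.96 × 1.04) = 2.1% or Φ(−1.96 × 1.27) = 0.6%.

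**Alternative structure.** Heterogeneous Toeplitz contains every scenario above, so its SE ratio is 1.00 in each.

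**The case against.** The strongest reply is that this is a contingency behind a sound main analysis. The planned structure is unstructured, which imposes no equal variance, and an error needs both non-convergence and unequal variances. That stands, and it limits the point.

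Four stronger readings are tempting, and the SAP does not support them:

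- *That the SAP prescribes a homogeneous Toeplitz.* It uses the bare term. The common-variance form is the ordinary reading, and the one a programmer would likely fit, but the documented defect is that the type is unstated.
- *That non-convergence is likely.* The 210 parameters assume all 20 visits enter. A model to Day 8 would have 7 × 8 / 2 = 28, and a parameter count alone does not show failure. For viral load the fallback looks remote: 10 parameters (Days 2-5) or 28 (Days 2-8), with about 144 + 75 = 219 children planned at IA#3 and 294 at IA#4.
- *That the primary test is inflated.* Under rising variance it is conservative, and only slightly so if the primary model stops at Day 5.
- *That the Day 8 interval by itself decides the trial's course.* Futility at IA#3 and IA#4 also needs viral load to fall short, at least two clinical intervals to exclude the TV and none to exclude the MAV, in both populations. Enrichment needs at least two of four endpoints with conditional power below 50%. Day 8 change alone triggers neither. It does feed the sample-size calculation, which covers all the clinical endpoints, but through conditional probabilities from normal-approximation contrasts.

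The assumed SDs show sensitivity, not a known bias. What remains is that the one structure held in reserve is poorly suited to outcomes whose spread probably changes over time.

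**Conclusion.** The point holds in conditional form. If the unstructured fit fails, and plain Toeplitz is fitted in its usual sense, and variances differ by visit, the Day 8 symptom SE can be about 10% too small or 11-14% too large on the assumed SDs. The 80% interval then covers about 75% or 85%, and the direction depends on a visit range the SAP leaves open. For the primary AUC to Day 5, under the assumed rise, the SE is overstated by about 4% (Days 2-5 model) or about 27% (Days 2-8 model), so the cost is power rather than false positives.

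These sizes rest on complete data, linear SD trends and assumed SDs and correlations; missing diaries would change them. Nothing here shows that the planned unstructured analysis is wrong. It is a weakness worth removing because removal costs almost nothing.

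**What to change.** In Sections 5.2.3 and 5.3.2.2, replace the fallback with an ordered list: heterogeneous Toeplitz (TOEPH) first, then heterogeneous AR(1) if that also fails. State in Section 5.3.2.2 which visits enter the symptom model; limiting them to those needed for Day 8 would also make the fallback less likely to be reached. It would help to list the visits in the primary viral load model too.

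The cost is a line in each section, a change of option in the code, and a few more variance parameters: for n visits, 2n − 1 instead of n, so 13 instead of 7 for Days 2-8.

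A homogeneous structure with an empirical (sandwich) variance as a last resort is optional. It does not combine directly with the planned Kenward-Roger method and may perform poorly with about 25 children per arm at IA#3.
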